8.6.5 Assessment of Poolability

Since this is a multi-center study, analysis will be performed by pooling data across study sites. The clinical study will be conducted under a common protocol for each investigational site, except for sites in Germany, where a separate protocol was used with different eligibility criteria, mainly related to the limits on liver function tests. It is expected that approximately 1% of the total number of patients randomized in the study will be from sites in Germany.

In the event that there are small sample sizes at some sites, sites may be grouped using the following procedure to create “analysis-sites” for analysis purposes. These analysis-sites will be created for North America, Europe, and Asia independently to preserve the ability to differentiate between regions. Patients from sites in Germany will not be included in this grouping mechanism. Analysis-sites are based on a target size of at least 5 patients per treatment group at each site. If investigative sites have at least 5 mITT patients per treatment group, they will retain their identities in the analysis. All investigative sites with fewer than 5 mITT patients per treatment group will be rank ordered by size and sorted secondarily by site identification number to break ties. Starting with the smallest investigative site, patients will be combined site by site by treatment group, until the first time the resulting analysis-site has at least 5 mITT patients in each treatment group. The process continues until all investigative sites are accounted for. If the last analysis-site has fewer than 5 mITT patients per treatment group, it will be combined with the most recently created analysis-site.

To assess the poolability of data across sites, a Cox regression analysis of the primary efficacy endpoint, OS, and all secondary time-to-event endpoints (i.e., TTP, TTUP, TTSP, TTDQoL) will be conducted including factors of treatment group, analysis-site, and treatment group by analysis-site interaction. Estimates of treatment effect and 95% CIs will be calculated separately by analysis-site.

Similarly, to assess the poolability of data across regions a Cox regression analysis will be conducted with analysis-site replaced by region. NB: region and study site will not be included simultaneously in the same model due to collinearity. Also, to assess the poolability of data across genders, a Cox regression analysis will be conducted with analysis-site replaced by gender. Patients from sites in Germany will not be included in these analyses.

Logistic regression of binary secondary endpoints (i.e., ORR and DCR) will be conducted using the same methodology described above for the Cox regression.

These analyses will be performed on the mITT population.

If, in the above analyses, the treatment group by analysis-site interaction, treatment group by gender interaction or treatment group by region interaction is statistically significant at a two-sided level of 0.15, the reasons for the observed differential treatment effect, such as patient demographic or clinical characteristics, will be investigated and reported. If the poolability of results is in direct question as a result of this sensitivity analysis, the endpoint(s) will also be analyzed separately by site, region, and/or gender.

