administered (mean, 1.8; range, 1-5). Toxicities included fatigue (57%), pain (23%), and nausea/vomiting (20%); 19% exhibited grade 3/4 bilirubin toxicity. The 30-day mortality rate was 3%. Response rates were 42% and 57% based on WHO and EASL criteria, respectively. The overall median TTP was 7.9 months (95% confidence interval, 6-10.3). Median survival times differed between patients with Child-Pugh A and B disease (A, 17.2 months; B, 7.7 months; $P = .002$). Patients with Child-Pugh B disease who had portal vein thrombosis (PVT) had a median survival of 5.6 months (95% confidence interval, 4.5-6.7). Baseline age; gender; performance status; presence of portal hypertension; tumor distribution; levels of bilirubin, albumin, and alpha-fetoprotein; and WHO/EASL response rate predicted survival. These investigators concluded that patients with Child-Pugh A disease, with or without PVT, benefited most from treatment. Patients with Child-Pugh B disease who had PVT had poor outcomes. TTP and overall survival varied by patient stage at baseline.

Hilgard⁸ et al report treatment of 108 consecutive patients with advanced HCC using TheraSphere. Median overall survival from day of treatment was 16.4 months for all patients, with median time to progression of 10.0 months. Tumor response at 90 days evaluated by RECIST in 62 patients were complete or partial response 10 (16%), stable disease 46 (74%) and progressive disease 6 (10%). Toxicities were generally mild to moderate with the most common being transient fatigue during the week following administration (61%) and abdominal pain (56%). One case of radiation cholecystitis was treated with cholecystectomy. There was no Grade 3 or 4 lung toxicities. Lymphopenia was observed without clinical sequelae. Because hepatic decompensation is a known risk of yttrium-90 microsphere therapy, all elevations in bilirubin values were considered to be treatment related hepatotoxicities. For patients with normal bilirubin at enrollment, 32% experienced Grade 1 or 2 elevations and three patients developed Grade 3 elevations. For patients with elevated bilirubin at enrollment, 17% experienced Grade 2 elevations and 30% experienced Grade 3 or 4 elevations. In the majority of patients, bilirubin returned to baseline values within 4-6 weeks. The authors conclude the therapy is safe and effective, even in patients with compromised liver function.

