8.6.4 Subgroup Analyses

Subgroup analyses of primary and secondary efficacy endpoints will be performed for the mITT population according to the subgroups listed in Section 7.7.

For each subgroup, a Cox proportional hazards model for time-to-event endpoints or a logistic regression for binary endpoints, will be fitted with treatment as the only covariate for each level of the subgroup separately.

For time-to-event endpoints, the HRs and associated 95% CIs will be summarized and presented on a forest plot, along with results of the overall analysis. If an endpoint has <10 events available at a subgroup level then the relationship between that subgroup level and endpoint will not be formally analyzed, since it is unlikely to be a meaningful analysis, and only descriptive summaries will be provided.

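### Site poolability of ORR and DCR: with analysis-sites as small as 5 per arm and no sparse-data rule, most site odds ratios for ORR cannot be estimated and the 0.15 interaction test is unreliable

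*SAP*

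**What the plan says.** SAP 8.6.5 sets the size of an analysis-site: "Analysis-sites are based on a target size of at least 5 patients per treatment group at each site". A site at or above that floor stays a separate level: "If investigative sites have at least 5 mITT patients per treatment group, they will retain their identities in the analysis". Smaller sites are combined only "until the first time the resulting analysis-site has at least 5 mITT patients in each treatment group", and the grouping itself is optional ("sites may be grouped using the following procedure to create").

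The Cox model for the time-to-event endpoints is specified as "including factors of treatment group, analysis-site, and treatment group by analysis-site interaction", with a treatment effect and 95% CI for each analysis-site. The binary endpoints follow the same route: "Logistic regression of binary secondary endpoints (i.e., ORR and DCR) will be conducted using the same methodology described above for the Cox regression". If the interaction with site, region or gender reaches a two-sided 0.15, the reasons are to be investigated.

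Section 8.6.5 does not say whether the interaction is tested by Wald, likelihood ratio or score. It does not say what happens when a site has no responders, or only responders, in an arm. The SAP has one sparse-data rule, in 8.6.4 ("If an endpoint has <10 events available at a subgroup level"), and it covers subgroup analyses of time-to-event endpoints only.

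**The concern.** A logistic model with treatment, site and their interaction is saturated: it fits a separate proportion to every site-by-arm cell. If a cell holds no responders, or only responders, its log-odds has no finite maximum-likelihood estimate, and the odds ratio for that site is infinite or undefined. With about 5 to 8 patients in a cell and a response rate well below 20%, empty cells are the usual case. DCR has the mirror problem if it is near 90%.

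Two outputs suffer. The site-level estimates and CIs cannot be produced at many sites. The 0.15 interaction test also loses its meaning, because its large-sample reference distribution does not apply to such cells. ORR is read by the investigator in an open-label trial with up to 105 centers, so differences between sites in reading response are what this check should be able to show.

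**Working it through.** The plan states no operating characteristic for this test, so there is no figure to reproduce.

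**Inputs from the documents**
- 520 patients randomized, 5% assumed ineligible and so outside mITT (SAP 4.4); about 1% at German sites, which are left out (SAP 8.6.5). 520 × 0.95 × 0.99 ≈ 489 in the model.
- Up to 105 centers (SAP 4.1): 489/105 ≈ 4.7 patients per center, so most centers would need grouping.
- The only RECIST rates given for TheraSphere are from a cited series of 62 evaluated patients (Protocol 5.3): 10 with complete or partial response (16%) and 46 with stable disease, so DCR 56/62 = 90%.

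**Assumptions**
- Control ORR 5-10%; DCR pairs 90% vs 70% and 80% vs 60% (treatment vs control).
- Applying the SAP grouping rule in simulation to 489 patients in 105 centers of uneven size gives about 30 analysis-sites with a median smaller arm of about 6. The mean is 489/30/2 ≈ 8 per arm. Hence 6 to 8 per arm below.

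**Share of sites without a finite odds ratio**

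For an arm of n with rate p, P(all or none respond) = d = (1−p)^n + p^n. For a site, P(odds ratio infinite or undefined) = 1 − (1−d_T)(1−d_C).

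| Treatment vs control | n = 6 per arm | n = 8 per arm |
|---|---|---|
| ORR 16% vs 5% | 1 − (1−0.351)(1−0.735) = 83% | 1 − (1−0.248)(1−0.663) = 75% |
| ORR 16% vs 10% | 1 − (1−0.351)(1−0.531) = 70% | 1 − (1−0.248)(1−0.430) = 57% |
| DCR 90% vs 70% | 1 − (1−0.531)(1−0.118) = 59% | 1 − (1−0.430)(1−0.058) = 46% |
| DCR 80% vs 60% | 1 − (1−0.262)(1−0.051) = 30% | 1 − (1−0.168)(1−0.017) = 18% |

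At the floor of 5 per arm the ORR figures are 87% and 76%. The grouping-rule simulation, with its mix of site sizes, gives 74% on average at 16% vs 5%.

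**Interaction test at 0.15**

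Simulated rejection rates (2000 runs, about 30 analysis-sites from the grouping rule, site baseline log-odds SD 0.3), for a between-site SD of the log odds ratio of 0 / 1 / 2:

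| Treatment vs control | Wald | Likelihood ratio |
|---|---|---|
| ORR 16% vs 5% | 0 / 0 / 0% | 9 / 35 / 80% |
| ORR 16% vs 10% | 0 / 0 / 0% | 28 / 71 / 97% |
| DCR 90% vs 70% | 0 / 0 / 0.6% | 31 / 78 / 99% |
| DCR 80% vs 60% | 0 / 1.7 / 4.9% | 42 / 91 / 100% |

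A valid test would show about 15% in the first position. In the Wald test, separated sites add degrees of freedom and almost no information. The likelihood-ratio statistic stays finite and responds to heterogeneity, but its null rejection rate is wrong in a direction that depends on the response rates.

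**Region-sized groups.** With three groups of 82 per arm, at most about 2.5% are separated when there is no heterogeneity. The Wald test then rejects 53% (ORR 16% vs 5%) and 63% (DCR 90% vs 70%) at SD 1.

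**The case against.** The strongest objection is that 8.6.5 names no statistic. The only Wald wording is in SAP 7.2, for the covariate models. A reader might infer that the site test cannot detect heterogeneity, so that its trigger would practically never fire. The documents do not support that. A likelihood-ratio test is equally compatible with the text and does react to heterogeneity; its fault is miscalibration, often firing too readily. The Wald test is not always blind either: with site sizes more concentrated and DCR 70% vs 50%, it rejects up to 44%.

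A reader might also infer that site heterogeneity in response would go unexamined and poolability be declared whatever the data show. The trigger in 8.6.5 also covers region and gender, where cells are far larger, and the SAP does not say that a non-significant result will be reported as proof of poolability.

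The DCR argument is weaker than the ORR argument. The 90% comes from a small evaluated series, whereas this trial counts patients without a post-baseline scan as non-responders, which lowers DCR. SAP 6.4.3.2 also lists DCR as an additional variable.

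Finally, the protocol's own poolability analysis (10.2.5) is of OS, and no success criterion depends on the response analysis. All of this stands and limits the point. It does not supply the missing site estimates or a valid test.

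**Conclusion.** The point holds as a defect in a supportive sensitivity analysis. Under the assumptions above, about 57-83% of site odds ratios for ORR are infinite or undefined. For DCR the share is about 46-59% at 90% vs 70% and 18-30% at 80% vs 60%. The site interaction test at 0.15 is unreliable whichever common statistic is chosen: for ORR, Wald rejects about 0% even at a log odds ratio SD of 2, while the likelihood-ratio test rejects roughly 5-40% with no heterogeneity.

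The sizes rest on assumed site sizes and control rates, and larger sites or mid-range rates reduce them. The region and gender models are much less affected, and OS poolability, analyzed by Cox regression, is untouched.

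**What to change.** In SAP 8.6.5, for ORR and DCR by analysis-site only:
- Replace the fixed-effect interaction test with an exact conditional test of homogeneity of odds ratios (Zelen type, Monte Carlo p-value), keeping the 0.15 level. A conditional resampling test of this kind, on 30 sites of 8 per arm with ORR 16% vs 10%, rejected 11%, 63% and 99% at SD 0, 1 and 2 (300 simulated trials).
- Report responder counts and proportions by arm for each site. Give a site odds ratio only where both arms have at least one patient with and one without the outcome.
- Keep the fixed-effect logistic model for region and gender.

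The threshold of 10 in 8.6.4 should not be carried over as a count of responders. At 8 per arm with ORR 16% vs 10%, the chance of 10 or more responders at a site is about 0.000005, so essentially every ORR estimate would be suppressed. A count of responders would not protect DCR, where patients without the outcome are the scarce ones.

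The cost is SAP wording and a short program, with no new data. Most site-level ORR odds ratios would no longer be tabulated, but they could not be estimated in any case.

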8.6.6 Additional Efficacy Analyses

All the additional analyses will be performed on both the mITT and PP populations.

DCR according to RECIST 1.1 by investigator assessment will be analyzed in the same way as ORR.

PFS according to RECIST 1.1 by investigator assessment is defined as the time from date of randomization until date of PD determined by investigator assessment, according to RECIST 1.1, or death due to any cause, whichever is earlier.

Progression-Free Survival (months) = (Date of event/censor – Date of Randomization +1) /30.4375.

The censoring of PFS is performed in the following order:

- 1) If a patient does not have a baseline tumor assessment, then the PFS time will be censored at the randomization date, regardless of whether or not PD or death has been observed.
- 2) If a patient received a subsequent HCC therapy before PD or death or in the absence of PD or death, the PFS time will be censored at the last valid (i.e. evaluable) post baseline radiological tumor assessment on or before the start date of the subsequent HCC therapy. If the patient has no valid post-baseline radiological tumor assessments on or before the start date of the subsequent HCC therapy, the patient will be censored at the randomization date.
- 3) If a patient is known not to have died or have PD and did not receive subsequent HCC therapy, the PFS time will be censored at the last valid post baseline radiological tumor assessment date or at the randomization date if the patient does not have any valid post-baseline radiological tumor assessments.
- 4) If a patient had PD immediately after two or more missed visits (Note: a response of NE for a visit is not considered as a missed visit), the patient will be censored at the time of the last valid post baseline radiological tumor assessment date that occurred before the missed visits. If the patient has no valid post-baseline radiological tumor assessments before the missed visits, the patient will be censored at the randomization date.

- Given the scheduled visit scheme of tumor assessments (i.e. every 8 weeks), the definition of 2 missed visits will equate to 16 weeks since the previous tumor assessment, or since the randomization date if no previous post-baseline tumor assessment.

PFS rates will be derived from the Kaplan-Meier estimates for each treatment group; 3, 6, 9, and 12-month TTP rates will be presented, together with 95% CIs. Quartiles will be presented and 95% CIs will be calculated on the quartiles for each treatment group. A log-rank (two-sided) test will be used to compare TTP between the two treatment groups at a 0.05 significance level. The HR and corresponding 95% CI will be computed from a Cox proportional hazards model. Plots of the Kaplan-Meier curves will be provided for each treatment group.

TPP, PFS, ORR and DCR, according to mRECIST criteria by blinded central image review, will be analyzed in the same way as the corresponding analysis of investigator assessed data described above.

Duration of objective response and duration of disease control by both blinded central image review and investigator assessment will be summarized by descriptive statistics (n, mean, SD, median, min, and max) by treatment group. Also, Kaplan-Meier analyses of duration of objective response and duration of disease control will be conducted.

Duration of response (months) = (Date of PD or death in absence of PD/Censor – Date of first overall response of CR or PR +1) /30.4375.

Duration of disease control rate (months) = (Date of PD or death in absence of PD/Censor – Date of first overall response of CR, PR or SD +1) /30.4375.

The censoring for duration of response and duration of disease control will be performed as follows:

- 1) If a patient received a subsequent HCC therapy before PD or death, or in the absence of PD or death, the duration of response and duration of disease control will be censored at the last valid post baseline radiological tumor assessment on or before the start date of the subsequent HCC therapy.
- 2) If a patient is known not to have died or have PD and did not receive subsequent HCC therapy, the duration of response and duration of disease control will be censored at the last valid post baseline radiological tumor assessment date.
- 3) If a patient had PD or died immediately after two or more missed visits (Note: a response of NE for a visit is not considered as a missed visit), the duration of response and duration of disease control will be censored at the time of the last valid post baseline radiological tumor assessment date that occurred before the missed visits. Given the scheduled visit scheme of tumor assessments (i.e. every 8 weeks), the definition of 2 missed visits will equate to 16 weeks since the previous tumor assessment.

DoR by both blinded central image review and investigator assessment will be summarized by descriptive statistics (number of patients, mean, standard deviation, median, minimum, and maximum) by treatment group. The number and percentage of patients achieving DoR with >10% tumor replacement by blinded central review and >20% tumor replacement by blinded central review will be summarized by treatment group. A 2-sample t-test will be performed to compare the mean DoR between treatment groups, and the corresponding 95% CI for the mean difference between the two treatment groups will be calculated.

PTTS by both blinded central image review and investigator assessment will be summarized by number and percentage of patients by treatment group at Week 8, 16, and 24. The 95% CIs for the PTTS rate for each of the treatment groups will be computed according to Wilson approach⁷. The PTTS rates will be compared between treatment groups using the continuity adjusted Wald test, and the corresponding 95% CI for the difference in PTTS rates between the two treatment groups will be calculated.

The percentage and absolute change from baseline in the sum of the longest diameters of target lesions on or before the start date of subsequent HCC therapy will be summarized separately at Week 8, 16, and 24 analysis visits (as defined in Table 3). A waterfall plot of the best percentage change in the sum of longest diameters for the best overall response will be presented.

The tumor marker for HCC (AFP) will be summarized with descriptive statistics (number of patients, mean, standard deviation, median, minimum, and maximum) for each time-point and change from baseline by treatment group. The number and percentage of patients achieving an AFP response, defined in Section 6.4.3.11, will also be summarized and compared between treatment groups using the continuity adjusted Wald test.

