6.4.3.7 Duration of objective response

The duration of objective response will be determined for patients who have a best overall response of CR or PR. Duration of objective response is defined as the time from first date of overall response of CR or PR until date of PD, or death due to any cause, whichever occurs first. If a patient did not die or progress then the date of the last radiological assessment will be used in the calculation.

Duration of objective response will be assessed separately by investigator assessment by RECIST 1.1 and by blinded central image review by mRECIST.

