 - For example, if a patient had a tumor assessment at Week 8, but did not have tumor assessments at Weeks 16 and 24, and then had PD at the Week 32 assessment (i.e. after 2 missed visits), then the TTP time would be censored at the date of the Week 8 assessment.
 - Given the scheduled visit scheme of tumor assessments (i.e. every 8 weeks), the definition of 2 missed visits will equate to 16 weeks since the previous tumor assessment, or since the randomization date if no previous post-baseline tumor assessment.

* Note: Censoring at the date of death, in the above censoring rules, is according to US Food and Drug Administration (FDA) guidance⁸. However, a sensitivity analysis of TTP, excluding censoring at the date of death (i.e. censoring at the last valid post baseline radiological tumor assessment date instead) with all other censoring rules described above still used, will also be performed.

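### PFS censors a progression found after two missed visits but counts a death after the same gap, while duration of response and disease control censor both

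*SAP*

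**What the plan says.** SAP 8.6.6 defines investigator PFS as time from randomization to progression "or death due to any cause, whichever is earlier". Four censoring rules follow, applied in order.

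- Rule 1 needs a missing baseline scan.
- Rule 2 needs subsequent HCC therapy before the event.
- Rule 3 begins "If a patient is known not to have died or have PD", so it does not reach a patient who has died.
- Rule 4 begins "If a patient had PD immediately after two or more missed visits (Note: a response of NE for a visit" and censors at the last valid scan before the gap, or at randomization if there is none. Death is not mentioned.

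Duration of objective response (SAP 6.4.3.7) runs "until date of PD, or death due to any cause, whichever occurs first", and duration of disease control (6.4.3.8) has the same end. Their missed-visit rule, also in 8.6.6, begins "If a patient had PD or died immediately after two or more missed visits" and censors at the last valid scan.

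Time to deterioration in quality of life (8.6.3.2) also counts death as an event. Its missed-visit rule applies to any deterioration as defined there, so it covers death too.

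SAP 8.6.6 plans a two-sided log-rank test at 0.05 in the PFS paragraph (the sentence names TTP). It analyzes PFS by blinded central review under mRECIST in the same way. TTP (8.6.2.1) and TTUP (8.6.2.2) each have a sensitivity analysis on a censoring choice; PFS has none.

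**The concern.** Two patients with the same disease course and the same gap are classified differently according to whether a late scan was done. If the scan is done and shows progression, the patient is censored at the last scan before the gap, and the later death no longer counts. If it is not done, the death is an event on its own date. Better documentation therefore removes an event.

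The SAP also handles one death in two ways. A responder who dies unscanned after the gap is a PFS event, but is censored for duration of response.

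At stake is the classification of some patients in a between-arm PFS comparison in an open-label trial, with no planned analysis to show how much the rule matters. The rule 4 wording suits TTP, where death is not an event, and the PFS paragraph still refers to TTP rates. A carry-over from TTP is a plausible cause, but that is inference.

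**Working it through.** The SAP gives no event count, power or hazard ratio for PFS, so there is no PFS figure to reproduce. The check applies the rules to one patient and then simulates their effect.

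**Worked patient.** Formula from SAP 8.6.6: months = (date of event or censoring − randomization date + 1) / 30.4375. The patient has a baseline scan, no progression at Week 8, misses Weeks 16 and 24, receives no subsequent HCC therapy and dies at Week 34.

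- Scanned at Week 32 with progression: rule 4 censors at Week 8. (8×7 + 1)/30.4375 = 57/30.4375 = 1.87 months, censored.
- Not scanned at Week 32: no rule applies. (34×7 + 1)/30.4375 = 239/30.4375 = 7.85 months, event.
- Duration of response, if Week 8 was the first response: censored at Week 8 in both cases, that is, after 1 day.

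The SAP states that "the definition of 2 missed visits will equate to 16 weeks since the previous tumor assessment", but its TTP example in 8.6.2.1 goes from a scan at Week 8 to a patient who "then had PD at the Week 32 assessment (i.e. after 2 missed visits", a gap of 24 weeks. The worked patient has gaps of 24 weeks to the scan and 26 weeks to death, so the result does not depend on that difference.

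**Simulation.** Both arms have identical true hazards. Inputs:

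- 8-weekly scans (Protocol 9.2.16).
- Median time to progression 5.5 months, the sorafenib figure in Protocol 5.3.
- Assumed death hazard 0.02 per month before and 0.12 after progression (median OS about 11.5 months).
- A gap is more than 16 weeks since the last scan.
- 20,000 patients per arm. Arm A misses 5% of visits at random.

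The attendance rates are assumptions; the documents give none. Entries are the apparent PFS hazard ratio, arm B against arm A.

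| Arm B attendance | Rule 4 as written | Every event counted | Both censored | Written minus every event |
|---|---|---|---|---|
| misses 15% at random | 0.976 | 0.982 | 0.972 | −0.006 |
| misses 25% at random | 0.943 | 0.957 | 0.932 | −0.014 |
| misses 5%, and 5% per visit stop scanning | 0.889 | 0.889 | 1.033 | 0.000 |
| misses 5%, and 10% per visit stop scanning | 0.794 | 0.794 | 1.057 | 0.000 |

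With nearly all patients having an event, the standard error of each log hazard ratio is about √(4/40,000) = 0.01. The last column compares rules on the same simulated patients.

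That column is the asymmetry's own contribution. A separate simulation with other assumed rates put it at about 0.01 to 0.02 with scattered gaps. When patients stopped scanning, that simulation gave 0.922 as written against 0.921 with every event counted, and 0.882 against 0.880.

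The reason is mechanical. Rule 4 acts only when a later scan finds progression, and a patient who has stopped scanning has no later scan. Under the same hazards, with 20% of visits missed at random, 4.8% of patients have a progression censored by rule 4 and 1.6% die after a gap. With no random misses and 5% per visit stopping, the shares are 0% and 16.0%.

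**The case against.** The strongest defense is that the asymmetry is reasonable on its face. A progression first seen after a long gap has an unknown onset date, whereas a death date is known, and PFS is defined to include death from any cause. That is a fair argument for counting deaths. It does not explain why a known death stops counting once a late scan is done, or why duration of response takes the opposite line on the same two events.

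A reader might infer that rule 4 by itself creates a sizeable PFS difference, since hazard ratios of 0.79 to 0.92 appear in simulated arms where more patients stop scanning. The documents do not support that. They give no attendance rates and set the same 8-weekly schedule for both arms, and the same hazard ratios appear when every event is counted. The shift comes from undetected progression being dated at death, which affects any PFS that counts deaths.

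A reader might also expect that copying the duration rule into PFS would remove bias. It would not. With both events censored, the simulated hazard ratio is 1.02 to 1.09 when scanning stops and 0.91 to 0.97 with scattered gaps, because censoring those deaths is informative.

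Three further points stand:

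- Duration of response covers responders only and has no stated between-arm test, so the two rules are inconsistent but the two results need not contradict each other.
- Rule 2 already censors patients who start subsequent HCC therapy before the event, so fewer patients are exposed than in a simulation without such therapy.
- PFS is listed under additional efficacy variables (SAP 6.4.3), not among the secondary endpoints (6.4.2).

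**Conclusion.** The inconsistency is real and can be read directly from SAP 8.6.6. For the same gap, PFS censors progression and counts death, while duration of response and disease control censor both. For an affected patient the difference is large: censored at 1.87 months or an event at 7.85 months, depending on one scan.

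The asymmetry's effect on the hazard ratio is small: about 0.01 to 0.02 under assumed scattered gaps, and near zero when patients stop scanning. These sizes rest on assumed attendance and death rates, and on patients without subsequent HCC therapy. Overall survival and the listed secondary endpoints are unaffected. The point is worth correcting because the PFS comparison is tested at 0.05 and no analysis is planned that would show its dependence on this rule.

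**What to change.** Treat progression and death after a gap the same way in PFS, and report PFS both ways:

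1. With progression and death after two or more missed visits both censored at the last valid scan, matching the rule for duration of response and disease control.
2. With every progression and every death counted at its recorded date.

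Name in advance which is the main PFS analysis, and apply both to the investigator RECIST 1.1 and central mRECIST versions. In each simulated scenario tabulated above, the result under the written rule lies at or between these two, so the pair shows how far PFS depends on scan attendance.

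The cost is one changed SAP sentence and one extra PFS run for each version, on data already collected. The downside is that neither version is unbiased if attendance differs by arm: the first drops late deaths informatively, and the second dates undetected progression at death.
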